## **6.0 Number of Subjects**

Twenty participants with aphasia will be recruited for this study to account for attrition and screen failures. We ultimately aim to have 10 participants with aphasia complete the study. This sample size was

chosen because this is a feasibility/pilot study and 10 participants is a feasible sample that will allow us to gather preliminary data to aid in the development of the intervention. We will also recruit up to 10 care partners of participants with aphasia to participate in qualitative interviews after the intervention to gain their perspectives as well. Thus, a total of up to 30 participants will be recruited.

## 7.0 Setting

Assessment and treatment sessions will be conducted on MUSC's campus in a private treatment room at the College of Health Professions Building C. Screening/Baseline, Post-Treatment, and Follow-Up sessions will be conducted in-person. Treatment sessions will also be conducted in person; however, if necessary, treatment sessions can be conducted on Zoom. Qualitative interviews with care partners can also be conducted via Zoom if care partners are unable to attend in person and would like to partake in the qualitative interview.

## 8.0 Recruitment Methods

This study will recruit from the Registry for Stroke Recovery (RESTORE-Pro#00037803, IRB approved 9/6/14) which is a research tool sponsored by the National Institutes of Health (NIH) Center of Biomedical Research Excellence (COBRE) in Stroke Recovery with subjects consented for future contact to support stroke recovery research conducted at MUSC. RESTORE staff will query the registry for potential subjects and provide the Principal Investigator (PI) with the contact information of subjects who meet their criteria. The PI or research staff will contact subjects to further screen for potential enrollment.

We will also recruit participants through local advertisement (flyers) in local acute care/inpatient hospitals and outpatient rehabilitation clinics, including the MUSC CARES Medical Clinic. Local speech-language pathologists will be informed about the study and given flyers so they can inform their patients with aphasia about the study. If their patients express interest in participating and give permission to the SLP to share their contact information (name, phone number, and or email) to be contacted by study personnel, the SLP may send their name and contact information to the PI, [name] [name], who will then contact the patient to give more information and confirm their interest. Otherwise, interested parties can contact the PI via email or phone as listed on the flyer. We will also recruit participants from local stroke and aphasia support groups by attending in person to inform attendees about the study and/or by passing out flyers at meetings. A sign-up list at these meetings will be available for people interested in being contacted directly about the study (requesting name, email, and phone number). Otherwise, interested parties can contact the PI via email or phone as listed on the flyer.

Care partners of participants with aphasia will be recruited for qualitative interviews by asking them whether or not they want to participate in the interview. Only care partners of enrolled participants with aphasia who complete the intervention will be asked to participate.

## 9.0 Consent Process

Written informed consent will be obtained from all participants with aphasia in person at the start of the first screening/assessment session by a member of the study team in a private room. A member of the study team will go through the entire form with the participant to explain the study in lay terms and answer any questions, and the participant will be given the opportunity to read through the consent form as well. They will be informed that they may choose to withdraw from the study at any time and their decision will not affect their clinical care in any way. If the participant agrees to participate in the study, they will sign and date the combined informed consent and HIPAA authorization. A copy of the signed form will be provided to participants.

Care partners of aphasia will be invited to participate in the interview to get their perspectives on the intervention. The purpose of the qualitative interview will be provided along with a description of what their participation would entail. If care partners are interested in participating in the interview, they will provide verbal agreement to participate. We will request a waiver of signed consent for this group.

## 10.0 Study Design / Methods

This study is a within-subject, pre-post, repeated measures, mixed-methods design to test the feasibility and acceptance of a psychosocial intervention for people with post-stroke aphasia and to gather preliminary data on its efficacy on improving psychosocial outcomes and retention/adherence to speech therapy. Quantitative primary and secondary outcomes will be administered before and after the intervention and at 1-month follow-up. In addition, qualitative data (questionnaire and interviews) will be collected at the end of the intervention to assess feasibility, acceptance, effects on retention/adherence to speech therapy, and to aid in refinement of the intervention. This includes semi-structured interviews that will be administered to participants with aphasia and care partners. Screening/Baseline, Post-Treatment, and Follow-Up sessions will be conducted in-person. Treatment sessions will also be conducted in person; however, if needed for personal circumstances, treatment sessions can be conducted on Zoom. Qualitative interviews with care partners can also be conducted via Zoom if care partners are unable to attend in person. A full description of all sessions is provided below and a summary of sessions are provided in Table 2 below. In general, if participants get fatigued or emotion at any point during testing or the intervention, breaks will be provided and emotional support will be provided by research personnel, if appropriate.

**Screening/Baseline Visit:** This session will last approximately 2 hours and consist of obtaining consent for the study, testing for inclusion/exclusion criteria, gathering personal history, and getting to know the participant/establishing rapport. If, based on the completed screening tasks, participants are appropriate for the study, they will be evaluated for psychosocial functioning, communication confidence, and cognition.

The following measures will be administered in the first session:

- Screening assessments
  - Questionnaire (demographic variables, personal/medical history, speech therapy history, psychological history)
  - Western Aphasia Battery-Revised (WAB-R; Kertesz, 2007)
  - Request medical records
- Psychosocial assessments
  - Hospital Anxiety and Depression Scale (HADS; Zigmond & Snaith, 1983)
  - Dynamic Visual Analog Mood Scale (D-VAMS; [http://dvams.com/dvams/menu\\_home\\_dvams.htm](http://dvams.com/dvams/menu_home_dvams.htm); Barrows, 2013)
  - Stroke Aphasia Depression Questionnaire-10 (SADQ-10; Sutcliffe & Lincoln, 1998)
  - Behavioural Outcomes of Anxiety Scale (Kneebone et al., 2012; Linley-Adams et al., 2014)
  - Simple Aphasia Stress Scale (SASS; Laures-Gore & Rice, 2019)

- Modified Perceived Stress Scale (mPSS; Hunting Pompon et al., 2018)
- Stroke Aphasia Quality of Life (SAQOL-39; Hilari et al., 2003)
- Communication Confidence Rating Scale for Aphasia (CCRSA; Cherney et al., 2011; Babbitt et al., 2011)
- Cognitive Assessment Scale for Stroke Patients (Barnay et al., 2012, 2014)

All assessment data will be collected via a secure data capture platform or on paper. The D-VAMS is an online-based assessment tool and data from that assessment will be exported to an .xml file and saved on the MUSC Network a cloud-based storage account to which only research personnel have access. Medical records will be reviewed to confirm the participant meets inclusion/exclusion criteria. Given that it may take time to obtain medical records to confirm eligibility (if the participant was not treated at MUSC for their stroke), if participants meet the rest of the eligibility criteria based on the questionnaire and WAB-R, then we will proceed with the remainder of the assessments in the Screening/Baseline session and confirm eligibility via medical records after the session.

**Session 1:** Session 1 will be scheduled once medical records are obtained and the participant's eligibility is confirmed. If possible, Session 1 will be scheduled within the same week as the first session and will last about 30 minutes. This session will focus on psychoeducation and an introduction to behavioral activation therapy. See detailed agenda for intervention sessions in Section 3 above entitled "Intervention to be studied".

**Sessions 2-5:** Session 2 will be scheduled approximately 1 week after Session 1 and following sessions will be held weekly. Each intervention session will last about 30 minutes. See detailed agenda for intervention sessions in Section 3 above entitled "Intervention to be studied".

**Session 6 (Post-Treatment Testing):** The post-treatment testing session will last approximately 2 hours and will consist of conducting all primary and secondary quantitative outcomes. Participants will also fill out a questionnaire with information about whether they were enrolled in speech therapy during their participation, whether they attended sessions and did their home programming. Finally, we will conduct a semi-structured qualitative interview to gather information about how feasible the intervention was for participants, their perceptions/opinions about it, and what they might want to see included that was not included.

The following assessments will be administered at the post-treatment testing session:

- Assessments
  - Hospital Anxiety and Depression Scale
  - Dynamic Visual Analog Mood Scale
  - Stroke Aphasia Depression Questionnaire-10
  - Behavioural Outcomes of Anxiety Scale
  - Simple Aphasia Stress Scale
  - Modified Perceived Stress Scale
  - Stroke Aphasia Quality of Life
  - Communication Confidence Rating Scale for Aphasia
- Questionnaire about retention/adherence to outpatient speech therapy

- Qualitative interview regarding perceptions of intervention with participants with aphasia and their care partners

Interviews will be audio recorded and transcribed for analysis. Audio recordings will be made on a Sony digital recorder and transferred immediately after the session to an MUSC Network computer or a cloud-based storage account to which only research personnel have access. Once transferred, audio recordings will be deleted off the recording device.

**Weekly check-in phone calls:** For the period of time between Session 6 (post-treatment) and Session 7 (1-month follow-up), we will conduct three weekly phone calls with the participant and/or the care partner to discuss behavioral activation activities and problem solve any issues they are having with completing pleasant/scheduled activities.

**Session 7 (1-month Follow-Up):** The following assessments will be administered at the 1-month follow-up testing session:

- Assessments
  - Hospital Anxiety and Depression Scale
  - Dynamic Visual Analog Mood Scale
  - Stroke Aphasia Depression Questionnaire-10
  - Behavioural Outcomes of Anxiety Scale
  - Simple Aphasia Stress Scale
  - Modified Perceived Stress Scale
  - Stroke Aphasia Quality of Life
  - Communication Confidence Rating Scale for Aphasia
- Qualitative interview regarding perceptions of intervention with participants with aphasia and their care partners

Again, qualitative interviews will be audio recorded and data will be handled the same way as for the post-treatment session.

Table 2. Schedule of Sessions

Session	Week	Description
Screening/Baseline	1	Consent Screening Pre-testing on primary & secondary outcomes
1	1	Daily assessments Psychosocial intervention
2	2	Daily assessments Psychosocial intervention
3	3	Daily assessments Psychosocial intervention

4	4	Daily assessments Psychosocial intervention
5	5	Daily assessments Psychosocial intervention
6	5	Post-testing on primary and secondary outcomes Retention/adherence to speech therapy questionnaire Qualitative interview
n/a	7	Weekly check-in call
n/a	8	Weekly check-in call
n/a	9	Weekly check-in call
7	10	1-month follow-up testing on primary and secondary outcomes Qualitative interview

To compensate participants with aphasia for their time and transportation costs, they will be paid \$40 per session. If they participate in all 8 sessions, they will earn \$320. Payment for study visits will be made using a pre-paid debit card, called a ClinCard. Participants will be given a ClinCard at the beginning of the study. After each session they participate in, they will receive \$40 payment. Care partners of participants with aphasia will not be compensated for their participation in the interviews.

## 12.0 Data Management

With 10 participants with aphasia, we are statistically powered to conduct feasibility analyses. For our primary quantitative analysis, we plan to conduct paired-samples *t*-tests to compare each outcome measure with 2 time points: baseline vs. post-treatment and baseline vs. 1-month follow-up. Baseline vs. post-treatment comparisons will be used to examine preliminary effects of the intervention on our primary outcome measures (HADS depression scores, HADS anxiety scores), and the secondary outcome measures listed above. Baseline vs. 1-month follow-up comparisons will be used to examine any delayed or maintained treatment effects on the primary and secondary outcome measures. Quantitative feasibility data and psychosocial data will also be examined descriptively given the small sample size.

Data gathered from the retention/adherence to speech therapy questionnaire and the semi-structured interview will also be analyzed descriptively and qualitatively for emergent themes that can be used to further refine and develop the psychosocial intervention.

To maintain participant confidentiality, all participants will be given a participant study ID which will be used on all their study documents and data. Participant names and direct identifiers will be stored separately from collected data and participant names and study IDs will be linked in one password-protected document saved on an MUSC Network computer or cloud-based storage account. Data will be stored in a secure data capture platform, on an MUSC Network computer or cloud-based storage account, and/or on paper in a locked file cabinet in a locked room on campus to which only research personnel have access. Interviews will be audio recorded and transcribed

for analysis. Audio recordings will be made on a Sony digital recorder and transferred as soon as possible after the session to an MUSC Network computer or a cloud-based storage account to which only research personnel have access. Once transferred, audio recordings will be deleted off the recording device. Consent forms will be stored separately from the data collected in a locked file cabinet in a locked room to which only relevant study personnel have access.

The RESTORE registry (Pro#00037803), from which this study will recruit subjects, also serves as a data analysis tool by which interdisciplinary teams may share data across projects and provide MUSC's stroke recovery research community with a more complete registry with key stroke elements. Some subjects may have participated or will participate in other stroke related research studies at MUSC. Sharing data from this and other stroke research studies with RESTORE will allow for more targeted recruitment efforts in the future and could reduce the burden placed on subjects by reducing the duplicative efforts of collecting common data and physical function assessments requested by multiple studies and storing them in one centralized and secure location. The third Aim of this study leverages this ability, as other studies will be better able to target their recruitment based on the information collected in these assessments. Subjects are informed in the consent process if they enroll into the RESTORE registry, their data from this study will be shared. They are given the option to do so or not in the consent form. Subjects will be asked to sign a HIPAA authorization stating their health information may be disclosed to MUSC investigators requiring their data for their research projects upon approval by an Institutional Review Board.

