**1.0 Objectives / Specific Aims**

The aim of this pilot project is to collect preliminary data on the feasibility, acceptance, and efficacy of an SLP-administered psychosocial intervention for people with post-stroke aphasia. The main objective of this pilot project is to determine whether the intervention is feasible and acceptable to participants with aphasia and their care partners, and we predict that it will be. Regarding the efficacy of intervention itself, we hypothesize that the psychosocial intervention will result in lower levels of psychosocial impairment (e.g., symptoms of anxiety and depression, chronic stress), better quality of life, and better retention and adherence to rehabilitation activities (i.e., attending therapies).

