**Intervention Session 1:** Session 1 will last approximately 30 minutes and focus on psychoeducation and an introduction to behavioral activation therapy. Session agenda:

- **Assessments (5 minutes):**
  - Hospital Anxiety and Depression Scale (HADS; Zigmond & Snaith, 1983)
  - Dynamic Visual Analog Mood Scale (D-VAMS; [http://dvams.com/dvams/menu\\_home\\_dvams.htm](http://dvams.com/dvams/menu_home_dvams.htm); Barrows, 2013)
  - Simple Aphasia Stress Scale (SASS; Laures-Gore & Rice, 2019)
- Participants will receive psychoeducation focused on (10 minutes):
  - normalizing the participant's psychosocial symptoms (e.g., loss of identity, depression, anxiety) and emotions (e.g., grief, anger, guilt, fear, embarrassment, etc.), which are common after stroke.
  - Discuss common effects of stroke/aphasia on daily life (e.g., social isolation, relationships, work, daily activities).
  - Discuss ways that depression, anxiety, or low mood can affect rehabilitation (e.g., attendance, homework completion, low engagement/motivation, perhaps less neuroplasticity)
- Participants will be introduced to the concept of behavioral activation therapy and the goal to increase the number of enjoyable activities that the participant partakes in. Participants will be asked what types of activities they enjoyed before their stroke, the activities/roles in their lives that they value, and the barriers they've faced to engaging in these activities. A list will be started of activities they enjoy/value and used throughout the intervention. (15 minutes)
- **Homework:** activity monitoring for participants to track how they currently spend their time and their mood during each activity with the help of a care partner if available.

**Intervention Session 2:** This session will last about 35 minutes and will consist of ongoing behavioral activation therapy and education on sleep hygiene.

- Assessments: HADS, D-VAMS, SASS (5 minutes)
- The SLP will go over the activity monitoring assignment with the participant and schedule valued/prefereed activities with the participant for the following week. Participants and the SLP will collaboratively problem solve as concerns about ability to engage in preferred activities arise. (20 minutes)
- The SLP will educate the participant on the importance of sleep and sleep hygiene practices that can improve sleep. The SLP will suggest ways the participant can instill proper sleep hygiene into their routine. (10 minutes)

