## 4.0 Study Endpoints (if applicable)

### Primary Outcome:

The primary outcome measure will be HADS, which is a conventional, validated, and widely used measure of psychosocial functioning. This scale consists of 14 items, seven of which contribute to a depression scale and seven that contribute to an anxiety scale. Therefore, three scores can be derived from this measure: an overall score, depression score, and anxiety score. The overall score will be used as the primary outcome measure and this measure will be administered at baseline, at each weekly psychosocial intervention session, post-treatment, and at 1-month follow up.

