### Secondary Outcomes:

Secondary measures of psychosocial functioning that are specifically validated for the aphasia population will be administered as well, including the D-VAMS, SASS, Stroke Aphasia Depression Questionnaire-10 (SADQ-10; Sutcliffe & Lincoln, 1998), Behavioural Outcomes of Anxiety Scale (BOA; Kneebone et al., 2012; Linley-Adams et al., 2014, Modified Perceived Stress Scale (mPSS; Hunting Pompon et al., 2018), Stroke Aphasia Quality of Life (SAQOL-39; Hilari et al., 2003), and Communication Confidence Rating Scale for Aphasia (CCRSA; Cherney et al., 2011; Babbitt et al., 2011). Most of these will be administered at baseline, post-treatment, and at 1-month follow-up (see below for a table with the timepoints for each measure and the rationale for inclusion). Two of these outcome measures will be also administered at the weekly sessions, including the D-VAMS and SASS.

A questionnaire related to attendance, retention and adherence to outpatient speech therapy services will also be collected at post-treatment to gather preliminary data on whether the psychosocial intervention was associated with good retention/in/adherence to rehabilitation activities. This will be done by administering a questionnaire to participants asking questions about whether they are receiving rehabilitation therapy, and if so, whether they have been attending and following recommendations.

Qualitative interviews will also be conducted at post-treatment and 1-month follow-up to aid in intervention refinement as well. Care partners of participants (e.g., family, friends, spouse) will be invited to participate in the interviews as well.

Table 1. Study Measures

Test Name	Construct	Timepoints	Justification
Primary			
Hospital Anxiety and Depression Scale (HADS)	Measures presence of signs/symptoms of depression and anxiety	All sessions	Overall assessment of psychosocial functioning
Secondary			
Dynamic Visual Analog Mood Scale (D-VAMS)	Measures mood based on reported feelings for 7 scales of emotion	All sessions	A weekly measure of mood fluctuations throughout the study
Simple Aphasia Stress Scale (SASS)	Measures perception of current stress level	All sessions	A weekly measure of acute stress

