Stroke Aphasia Depression Questionnaire-10 (SADQ-10)	Measures presence of signs/symptoms of depression in people with aphasia	Screening/Baseline, Post-treatment (Session 6), 1-month follow-up (Session 7)	Aphasia-validated measure of depression to compare with HADS outcome
Behavioural Outcomes of Anxiety Scale	Measures presence of signs/symptoms of anxiety	Screening/Baseline, Post-treatment (Session 6), 1-month follow-up (Session 7)	Aphasia-validated measure of anxiety to compare with HADS outcome
Modified Perceived Stress Scale (mPSS)	Measures perceived levels of stress in people with aphasia	Screening/Baseline, Post-treatment (Session 6), 1-month follow-up (Session 7)	Aphasia-validated measure of chronic stress to compare with other measures of psychosocial functioning

Stroke Aphasia Quality of Life (SAQOL-39)	Measures overall quality of life in people with aphasia	Screening/Baseline, Post-treatment (Session 6), 1-month follow-up (Session 7)	Aphasia-validated measure to examine whether intervention has an effect on quality of life
The Communication Confidence Rating Scale for Aphasia (CCRSA)	Measures how confident people with aphasia are at communicating in a range of scenarios	Screening/Baseline, Post-treatment (Session 6), 1-month follow-up (Session 7)	Aphasia-validated measure to examine whether intervention has an effect on communication confidence
Other Standardized Assessments			
Western Aphasia Battery-Revised (WAB-R)	Measures language abilities	Screening/Baseline	To determine eligibility for study and acquire language profile
Cognitive Assessment Scale for Stroke Patients	Measure cognitive abilities	Screening/Baseline	To examine relationships between cognition and primary/secondary outcome measures
Qualitative Assessments			
Rehabilitation Retention & Adherence	Measure whether they have been participating in rehabilitation activities and adhering to recommendations	Post-treatment (Session 6)	To determine whether psychosocial intervention may have had positive impact on rehabilitation retention/adherence
Participant and Care Partner Acceptability of Psychosocial Intervention	Measure participant and care partners' perceptions about psychosocial intervention	Post-treatment (Session 6), 1-month follow-up (Session 7)	To identify acceptability of the intervention by participants and their care partners and to refine intervention to meet patient needs

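### The paired t-tests will by default use only people with both scores and leave out the session-by-session HADS already collected; one sensitivity analysis and a small table of leavers would cheaply strengthen the secondary efficacy aim

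*Combined protocol and SAP*

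**What the plan says.** **Aim.** Section 1.0: "The main objective of this pilot project is to determine whether the intervention is feasible and acceptable". Efficacy is a preliminary, secondary aim.

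**What is measured.** For the HADS, Section 4.0 says "The overall score will be used as the primary outcome measure" and that "this measure will be administered at baseline, at each weekly psychosocial intervention session, post-treatment, and at 1-month follow up". For two secondary scales, "Two of these outcome measures will be also administered at the weekly sessions, including the D-VAMS and SASS". The Session 1 agenda in Section 3.0 ("Session 1 will last approximately 30 minutes and focus on psychoeducation and an introduction to behavioral activation therapy. Session agenda") lists the three scales first, ahead of psychoeducation. Section 10.0 also gives all three at the Screening/Baseline visit. HADS, D-VAMS and SASS therefore each have two pre-treatment scores and a score at every later session. The other quantitative secondary scales have one pre-treatment score; the SADQ-10, for example, is listed in Table 1 as "Aphasia-validated measure of depression to compare with HADS outcome".

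**What is tested.** Section 12.0 names only paired t-tests, "to compare each outcome measure with 2 time points: baseline vs. post-treatment and baseline vs. 1-month follow-up", plus a descriptive look at feasibility and psychosocial data. It does not define baseline; Tables 1 and 2 point to the Screening/Baseline visit.

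**Who may be missing.** Section 6.0: "Twenty participants with aphasia will be recruited for this study to account for attrition and screen failures", with 10 intended to complete. No section gives a missing-data method, an analysis population, a sensitivity analysis or a comparison of leavers with completers.

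**The concern.** A paired t-test drops anyone without both scores. With no other rule stated, someone who starts treatment and leaves before Session 6 contributes nothing to the efficacy estimate, even though their HADS was recorded at every session they attended.

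In a single-arm pre-post design there is no control group in which the same loss could show up. If people who are getting worse are the ones who leave, the mean change in those who remain looks like benefit. Section 2.0 itself links depression and anxiety to poor retention in rehabilitation, and Section 15.0 foresees psychological discomfort during the intervention, so the pattern is plausible, though not shown.

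At stake is whether the preliminary effect carried into later development of the intervention is somewhat too favourable. A lesser matter is that the Session 1 score could show how far the result depends on a single pre-treatment reading.

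**Working it through.** **Inputs from the documents.** 20 recruited and 10 completers intended (Section 6.0); HADS at eight occasions, namely Screening/Baseline, Sessions 1 to 5, Session 6 and Session 7 (Table 2). There is no power calculation to reproduce: no alpha, effect size, SD, correlation or dropout rate is given.

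**Assumptions.** HADS overall SD 7 (range 4 to 9; every figure in points scales with it). The correlation between two scores is b + s·exp(−days/τ), plus residual error, with (b, s, τ) = (0.40, 0.50, 28), (0.60, 0.30, 21) or (0.30, 0.50, 40). This gives a Screening-to-Session 6 correlation r of 0.51 to 0.66. No true change. 12, 14 or 16 starters, about 10 completers.

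**1. Precision of the planned test.** The 95% half-width with 10 pairs is 2.262 × SD × √(2(1−r)/10). At r = 0.6 and SD 7: 2.262 × 7 × √0.08 = 4.5 points (2.6 at SD 4, 5.8 at SD 9).

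**2. Overstatement from selective dropout.** In simulation, people could leave after Sessions 2 to 5. The log-odds of leaving rose by 1.0 or 1.5 for each SD by which HADS had risen since Screening (1,000 trials per setting, simulation error 0.05 to 0.08 points).

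| Starters | False improvement at Session 6, SD 7 | In SD units |
|---|---|---|
| 12 | 0.5 to 0.9 | 0.07 to 0.13 |
| 14 | 0.9 to 1.6 | 0.12 to 0.23 |
| 16 | 1.1 to 2.0 | 0.15 to 0.28 |

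Against the 4.5-point half-width this runs from 0.5/4.5 = 11% to 2.0/4.5 = 44%. The nominal 5% false-positive rate becomes 6 to 14%.

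*Arithmetic check.* With 10 completers and k leavers, completer mean minus all-starter mean = k/(10+k) × (completer change − leaver change). Working back, 0.5 to 0.9 points with k = 2 implies a Session 6 gap of 6 × (0.5 to 0.9) = 3.0 to 5.4 points. With k = 6, (16/6) × (1.1 to 2.0) = 2.9 to 5.3. The two agree. The gap between leavers' change to their last score and completers' change to Session 6 is larger, about 4 to 8 points, because part of a leaver's rise would have faded by Session 6.

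**3. Other dropout patterns.** Random dropout: no bias beyond simulation error. Dropout driven by HADS level: about 0.2 points of false improvement at Session 6 and 0.1 to 0.6 of false worsening at Session 7.

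**4. What a model of all observed scores recovers.** Under the dropout in step 2:
- With a random intercept, serial correlation and residual error, it leaves about 0.1 points (0.2 or less in a smaller repeat), with a false-positive rate of 3 to 6%. However, a covariance parameter ended at its limit in 25 to 49% of trials, and in 27 to 52% of the repeat, where non-convergence was never reported.
- Without the random intercept it leaves 0.3 points or less. Its false-positive rate with complete data is 1.6 to 3.3%, so it is somewhat conservative.
- If leaving depends on the next, unseen score, the first of these models still leaves 0.6 to 0.9 of a 1.4 to 2.5 point bias at Session 6.

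**5. Averaging the two pre-treatment scores.** Let r12 be their correlation, and r1 and r2 the correlations of Screening and Session 1 with Session 6. The ratio of change variances is [1 + (1+r12)/2 − r1 − r2] / [2(1−r1)]. With Session 1 at day 3.5 and Session 6 at day 34:
- (0.40, 0.50, 28): (1 + 0.921 − 0.548 − 0.568)/0.904 = 0.89
- (0.60, 0.30, 21): (1 + 0.927 − 0.659 − 0.670)/0.682 = 0.88
- (0.30, 0.50, 40): (1 + 0.879 − 0.514 − 0.533)/0.972 = 0.86

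That is a fall of roughly 11 to 15%. At SD 7 the half-width goes from 4.1–4.9 to 3.9–4.6 points. A 25% fall (ratio 0.75) needs r12 = r1 = r2, meaning that scores days apart agree no better than scores five weeks apart. Averaging alone does not cure selective dropout: it leaves 0.4–0.8, 0.7–1.4 and 0.8–1.6 points with 12, 14 and 16 starters.

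**The case against.** The strongest reply is that this is a 10-person, single-arm pilot whose main question is feasibility and acceptability. Omitting sensitivity analyses there is not an error, and the planned descriptive look at the data could include retention counts and weekly HADS. That stands, and it is why the point is optional. But the descriptive sentence names no leavers, no Session 1 score and no missing Session 6 or 7 scores, and it would not correct the paired estimate.

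The size of the harm rests on an assumed mechanism. With 12 starters the false-positive rate is close to nominal, and random dropout does no harm. This also stands.

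A mixed model with a rich covariance is a lot to ask of 12 to 16 people. This stands for the version with a random intercept. The simpler version does about as well, so the remedy uses it.

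Some readers may go further than the documents allow:
- *That the plan prescribes a complete-pairs analysis.* It does not; this follows from the test and from silence on missing data.
- *That half of those treated will be lost.* The step from 20 to 10 combines screen failures with attrition, so loss after treatment starts is unknown.
- *That Screening/Baseline is the wrong baseline.* It is defensible: like Sessions 6 and 7 it is an in-person testing visit, whereas Session 1 is a shorter treatment session that may be held on Zoom. It is also the only pre-treatment time for the scales to be set beside the HADS.

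**Conclusion.** The point holds as an optional improvement to the secondary efficacy aim. The named tests leave out HADS scores that will already exist, and nothing planned would show whether leavers differ from completers. If people with rising HADS leave early, the paired change overstates improvement by about 0.5 to 2 points, given SD 7, 12 to 16 starters and about 10 completers. The figure scales with the SD. It is near zero under random dropout and about 0.2 points at Session 6 under level-driven dropout.

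A reader might infer that the planned efficacy result is biased. The documents do not support that: they say nothing about who will leave or why. What they support is that such a bias, if present, would go unchecked. The second pre-treatment score is a smaller matter, worth roughly an 11 to 15% fall in change variance under the covariances used, with 25% only an upper bound.

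**What to change.** **First**, reconcile Section 4.0, which makes the HADS overall score primary, with Section 12.0, which names the depression and anxiety scores. If the subscales are primary, fit the model below to each.

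**Keep** the paired t-tests as primary and state that baseline is the Screening/Baseline visit.

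**Add to Section 12.0:**
- *Sensitivity analysis of HADS.* A REML mixed model in all eligible participants who attended Session 1, using every observed score. Occasion (eight levels) is a fixed effect, with exponential serial correlation over actual visit dates and a residual error term. Leave out a random intercept from the start; if one is included, drop it whenever any covariance parameter ends at its limit, not only on non-convergence. Contrast Session 6 and Session 7 with Screening/Baseline, with 95% confidence intervals on (starters − 1) degrees of freedom, shown beside the paired results.
- *Counts.* The number who started treatment and the number lacking Session 6 or Session 7.
- *A small table, without a test.* Screening and last observed HADS of those who left before Session 6, beside Screening and Session 6 HADS of those who did not. A test would be uninformative: against 10 completers, 80% power needs a standardised difference of about 2.4 with 2 leavers and 1.7 with 5.
- *Optional.* Repeat the paired comparisons for HADS, D-VAMS and SASS with the mean of the Screening/Baseline and Session 1 scores. Use the Screening score alone where Session 1 was not scored before intervention content, and record whether Session 1 was in person or on Zoom.

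**Cost.** One extra model, a few counts, a small table and, if wanted, one repeated set of tests; no new visits or scales. The model assumes that dropout depends only on observed scores, and that assumption is confined to the sensitivity analysis.
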